2.3 Study Rationale

Provide the scientific rationale for the research.

The cause of long-term functional deficits remains unclear and is thought to be multifactorial. Changes in tendon length, area and mechanical properties, as well as muscle atrophy, are likely to play a role in the long-term deficits [30]–[32]. Significant changes in muscle pennation angle and fascicle length have been observed during the first 4 weeks post-injury [33]. Muscle atrophy rapidly develops within the first 6 weeks following ATR and does not significantly improve over time [16], [34]. Short-term atrophy is likely caused by reduced activity of the calf muscle, but long-term atrophy might be associated with tendon elongation [15]. Tendon elongation develops within the first 6 weeks following ATR and remains relatively constant after this point [35]–[37]. The timing of the adverse changes in the muscles and tendon coincides with the periods without weight bearing or partial weight bearing of current rehabilitation protocols [38]. In clinical practice the majority of rehabilitation protocols recommend no weight bearing for 2 weeks after repair, partial weight bearing starting from week 4, and full weight bearing at week 6 [39]. In studies using early functional rehabilitation, full weight-bearing is allowed during the first 2 weeks [21], however the patients report loading around 25% of bodyweight onto the injured side [40]. Additionally, weight-bearing does not guarantee muscles activation or tendon loading [41]. We propose to use neuromuscular electrical stimulation (NMES) to provide muscle activity and mechanical stimulus to the tendon during the weeks of reduced leg activity.

NMES can positively impact several of the factors affecting the recovery from ATR and has been successfully applied as part of rehabilitation protocols for knee surgery to preserve muscle volume and

[figure not shown]

Figure 2. Pad placements: I) medial gastroc, II) lateral gastroc, III) soleus, IV) full calf.

[figure not shown]

Figure 3. Force produced by different pad placements as function of intensity.

strength [42]–[45]. Therefore, NMES can attenuate muscle atrophy during the first weeks of recovery after ATR repair surgery. Abundant work in animal studies has shown that controlled loading immediately after rupture or repair enhances up-regulation of repair genes [46], increases the diameter of newly organized collagen [47], decreases occurrence of sensory neuropeptides in the tendon proper [47], and improves tendon strength [48]. In humans, early controlled loading improves mechanical properties of the Achilles tendon after rupture [36]. Consequently, NMES can also provide controlled tendon loading during the first weeks of recovery, likely improving the structural and mechanical properties of the healing tendon. Additionally, NMES significantly reduces the risk of deep vein thrombosis [49], a possible complication during recovery from ATR [50]–[52].

3.0 Inclusion and Exclusion Criteria

Create a numbered list below in sections 3.1 and 3.2 of criteria subjects must meet to be eligible for study enrollment (e.g., age, gender, diagnosis, etc.).

Vulnerable Populations:

Indicate specifically whether you will include any of the following vulnerable populations in this research. You MAY NOT include members of these populations as subjects in your research unless you indicate this in your inclusion criteria because specific regulations apply to studies that involve vulnerable populations.

The checklists referenced below outline the determinations to be made by the IRB when reviewing research involving these populations. Review the checklists as these will help to inform your responses throughout the remainder of the protocol.

- **Children** –Review “HRP-416- Checklist - Children”
- **Pregnant Women** – Review “HRP-412- Checklist - Pregnant Women”
- **Cognitively Impaired Adults**- Review “HRP-417- Checklist - Cognitively Impaired Adults”
- **Prisoners**- Review “HRP-415- Checklist - Prisoners”
- **Neonates of uncertain viability or non-viable neonates**- Review “HRP-413- Checklist - Non-Viable Neonates” or “HRP-414- Checklist - Neonates of Uncertain Viability”

[Do not type here]

3.1 Inclusion Criteria

Create a numbered list of the inclusion criteria that define who will be included in your final study sample (e.g., age, gender, condition, etc.)

Subjects: 50 participants will be recruited.

1. male and female participants,
2. Age 18-65,
3. Having a diagnosis of an acute complete Achilles tendon rupture and undergoing surgical repair.

3.2 Exclusion Criteria

Create a numbered list of the exclusion criteria that define who will be excluded in your study.

The exclusion criteria include:

1. Those unable to understand spoken English.
2. Participants treated non-operatively
3. Augmented surgical repair (i.e., use of additional tissue at the repair site)
4. Tendon ruptures associated with the use of fluoroquinolones (Examples include ciprofloxacin (Cipro), gemifloxacin (Factive), levofloxacin (Levaquin), moxifloxacin (Avelox), norfloxacin (Noroxin), and ofloxacin (Floxin))
5. Allergy to ultrasound gel
6. Any other condition affecting the ability of the participant to walk or jump
7. Any other health conditions known to impair normal healing:
 - a. Diabetes
 - b. Cardiovascular conditions decreasing blood supply to the leg
8. Those unable to consent

3.3 Early Withdrawal of Subjects

3.3.1 Criteria for removal from study

Insert subject withdrawal criteria (e.g., safety reasons, failure of subject to adhere to protocol requirements, subject consent withdrawal, disease progression, etc.).

Subject participation will be discontinued by recommendation of the team physician ([name]) if the subject experiences excessive pain during stimulation (>5/10), excessive tendon elongation (>3 cm), gapping at the repair site (>5 mm) or other AEs. Participants will also be removed if the outcomes from the repair surgery require patients to deviate from the standard rehabilitation protocol. An additional criteria include failure of the subject to adhere to the protocol and subject consent withdrawal.

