1.3 Secondary Study Endpoints

State the secondary endpoints to be measured in the study.

Muscle volume, Achilles tendon length and area, steps, and self-reported outcomes VAS (pain), ATRS, FAOS, PAS, adverse events, and compliance to the proposed treatment.

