3.3.2 Follow-up for withdrawn subjects

Describe when and how to withdraw subjects from the study; the type and timing of the data to be collected for withdrawal of subjects; whether and how subjects are to be replaced; the follow-up for subjects withdrawn from investigational treatment.

Data collected up to the time of withdrawal may be used in the study. Subjects will be recruited until the desired number of participants with complete data points is reached. Subjects who experience AEs that are potentially related to the intervention will be followed via phone call or email to obtain information on how the AE resolves.

Participants who experience any of the above mentioned AEs will be followed up until resolved or stabilized.

Subject will be asked for consent to be contacted for possible future studies. Withdrawn subjects will be contacted if new information is available concerning the methods and techniques used in the study.

The subjects who withdraw from the study will not be replaced.

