7.4.4 Subject Compliance Monitoring

Insert the procedures for monitoring subject compliance.

The stimulation device provides an activity log that will be used to monitor compliance. Additionally, entries to the pain and activity diary will be also used to evaluate compliance.

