7.4.6.3 Preparation and Dispensing

Describe how the test article will be assigned to each subject and dispensed. Describe the steps necessary to prepare the test article. Include where the test article preparation will be done and by whom. Fully describe how the study treatment is to be administered and by whom.

The research team or clinician of the research team will demonstrate the NMES procedure to the participants. The research team will verify that the procedure is applied properly and corrects any problems with the protocol.

7.4.6.4

Return or Destruction of the Test Article

Describe the procedures for final reconciliation of the test article supply at the end of the study and whether the test article is to be shipped back to a source or destroyed on site.

At the week-6 visit, patients will return the stimulation device to a member of the study team.

7.4.6.5

Prior and Concomitant Therapy

Describe what prior and/or concomitant medical therapy will be collected. Describe which concomitant medicines/therapies are permitted during the study. Describe which concomitant medicines are not permitted during the study.

Patients can follow standard rehabilitation while using the stimulation device.

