8.3 Statistical methods

Describe the statistical methods (or non-statistical methods of analysis) that will be employed.

We will recruit 25 participants to participate in the NMES intervention and 25 for standard rehabilitation (control). Summary statistics for variables of interest including recruitment, retention, adherence, and reported pain will be calculated. To test the difference between groups (NMES and control), we will quantify the odds ratio and the 95% confidence interval of performing a single heel-rise test. If the bottom end of the confidence interval is higher than 1.0, the improvement will be significant. Chi-square goodness of fit will be used to study the associations between groups and covariates such as gender, activity, and age. Cochran-Mantel-Haenszel test will be used to evaluate the consistency of such associations.

Protocol deviations, such as missing visits, or lost to follow up (within the 10% already considered in the power analysis) will have a negligible effect on the statistical analysis since the proposed analysis can have unbalanced groups. The planned interim safety analyses will quantify the odds ratio between adverse events in the intervention group and standard of care. If the bottom end of the confidence interval is higher than 1.0, the incidence of AEs in the intervention group will be significant higher than that of standard care.

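### Failure to adhere is a ground for removal while compliance is a secondary endpoint, so reported adherence may be biased upward

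*Combined protocol and SAP*

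**What the plan says.** Section 1.1 gives initial feasibility of the NMES protocol as a purpose of the study. The secondary endpoints in section 1.3 end with "adverse events, and compliance to the proposed treatment". The analysis in section 8.3 is descriptive: "Summary statistics for variables of interest including recruitment, retention, adherence, and reported pain will be calculated". Neither section gives a compliance metric, a denominator or an analysis population.

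After the safety grounds, section 3.3.1 adds: "An additional criteria include failure of the subject to adhere to the protocol and subject consent withdrawal". It sets no level of adherence, no time point and no decision-maker.

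For people who leave, section 3.3.2 makes three statements. On what they have already contributed, it is permissive: "Data collected up to the time of withdrawal may be used in the study". On the recruitment target, it aims at complete records: "Subjects will be recruited until the desired number of participants with complete data points is reached". On replacement, it rules this out: "The subjects who withdraw from the study will not be replaced". The follow-up it plans for them concerns adverse events. No outcome visit after withdrawal is described.

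On measurement, section 7.4.4 says: "The stimulation device provides an activity log that will be used to monitor compliance". It adds that diary entries will also serve. Section 7.2.3 has the device exchanged at week 4 so that its memory can be compared with REDCap. The last hand-in is in sections 7.2.4 and 7.4.6.4: "At the week-6 visit, patients will return the stimulation device to a member of the study team".

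**The concern.** Adherence is an outcome of this trial, and a poor value of that outcome is also a reason to take the participant out. A summary of those who remain is then conditional on the quantity being summarised, and it errs in one direction. Retention is affected too, because it would mix people who chose to leave with people the team removed.

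The same rule can reach the primary endpoint. A participant removed before week 12 has no planned heel-rise test. The removal ground applies to both arms, but only the NMES arm has a device and a log on which low use could be seen. Loss from this cause could therefore be uneven between arms.

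Finally, the device log is the only source clearly described as recording NMES use. Nothing says how it, or the stimulator, is recovered from someone withdrawn between hand-ins.

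**Working it through.** **1. The plan's own figures.** The documents give no adherence rate, target or threshold, so there is no adherence figure to reproduce. The nearest figure is the attrition allowance in section 8.2: 22 / (1 − 0.10) = 24.4, rounded up to 25 per group. That leaves room for 25 − 22 = 3 losses per arm from all causes. Five removals in one arm would leave 20, below the stated minimum of 22.

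**2. Scheduled sessions (Table 2).** I assume daily use and count each daily application as one session.
- Week 1: 7 × 1 = 7. Weeks 2–3: 14 × 2 = 28. Weeks 4–6: 21 × 2 = 42. Total 77.
- Due by day 14: 7 + 7 × 2 = 21. Due by day 28: 7 + 28 + 14 = 49.

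**3. Illustration with removal at day 14.** Assumed, not from the documents: 25 in the NMES arm, retained participants complete 90% of sessions, and removed participants complete 40% until removal. Three summaries are all compatible with section 8.3:
- A, retained only: 90%.
- B, each person scored on sessions due until removal, averaged over 25. Five removed: (20 × 0.90 + 5 × 0.40) / 25 = 80%. Three removed: (22 × 0.90 + 3 × 0.40) / 25 = 84%.
- C, logged sessions over the full 77 for all 25. Five removed: (20 × 0.90 × 77 + 5 × 0.40 × 21) / (25 × 77) = 1428 / 1925 = 74.2%. Three removed: (22 × 0.90 × 77 + 3 × 0.40 × 21) / 1925 = 1549.8 / 1925 = 80.5%.

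The retained-only figure exceeds the all-randomised figures by 10 to 16 points with five removed, and by 6 to 9.5 points with three.

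**4. Sensitivity with other assumptions.** Retained participants at 85%; k of 25 removed at day 28 with adherence a of 20% to 40%.
- All-25 mean = [(25 − k) × 0.85 + k × a] / 25.
- Pooled to removal = [(25 − k) × 0.85 × 77 + k × a × 49] / [(25 − k) × 77 + k × 49].
- Full schedule = [(25 − k) × 0.85 × 77 + k × a × 49] / (25 × 77).

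| k | All-25 mean | Excess of retained-only 85% (points) | Pooled to removal | Full schedule |
|---|---|---|---|---|
| 2 | 79.8–81.4% | 3.6–5.2 | 81.6–82.6% | 79.2–80.2% |
| 3 | 77.2–79.6% | 5.4–7.8 | 79.8–81.4% | 76.3–77.9% |
| 5 | 72.0–76.0% | 9.0–13.0 | 76.1–78.8% | 70.5–73.1% |
| 8 | 64.2–70.6% | 14.4–20.8 | 70.0–74.6% | 61.9–65.9% |

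A retained-only summary overstates the all-25 mean by about 4 to 21 points. If data up to removal are kept and pooled, the overstatement falls to about 1 to 6 points (for example k = 2, a = 40%: 82.6 − 81.4 = 1.2; k = 8, a = 20%: 70.0 − 64.2 = 5.8). The result therefore depends on whether removed participants count and on which denominator is used, and the plan fixes neither.

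**5. Recovery of the log.** Table 3 allows the week-2 visit by video call, so the first hand-in is the week-4 exchange and the next is week 6. Section 7.4.6.4 deals only with week 6. No section covers withdrawal between these points.

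**The case against.** The strongest reply is that nothing in section 8.3 restricts the adherence summary to completers, and section 3.3.2 permits data from withdrawn participants to be used. That stands, and it is why the conclusion is that adherence may be biased. A reader might infer that the feasibility result will be inflated, but the documents do not support that: a retained-only summary is one possible analysis, not the stated one. Permission to use data is still not a commitment, and recruiting towards complete data points the other way.

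A reader might also infer that the device is collected only at week 6, or that anyone removed before week 4 leaves no adherence data. Neither holds. The week-4 exchange includes a memory check, diary data are gathered at weeks 2, 4 and 6, and section 7.2 mentions weekly checks at which the adherence meter might be read. These help only in part. The diary contents listed in section 7.2 are weight-bearing, steps and pain, not NMES sessions, and Table 3 has no visit in week 3 or 5.

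Third, the removal ground is generic and covers any protocol non-adherence in either arm; no section says that a low session count triggers it. That stands too. The point is that nothing prevents it, and low use is the obvious case in a trial of home stimulation.

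Fourth, the magnitudes are assumed, and five removals is twice the protocol's 10% attrition. Agreed: they show sensitivity and are not a forecast. Scoring zero after a physician-directed stop would also mix tolerability with adherence, so the fix separates the two.

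Section 8.3 treats losses within 10% as negligible because the analysis tolerates unequal groups. That answers unequal size but not selective loss.

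**Conclusion.** The concern holds as a defect in the rules, with a likely direction but no derivable size. Applied as written, section 3.3.1 can cut off low values of a secondary endpoint, and section 3.3.2 does not require that what was observed be used. Reported adherence may therefore be biased upward, and the week-12 heel-rise may be lost in the same participants.

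The only sizes available are illustrative: 90% against 74–80% if 5 of 25 are removed at day 14, and 90% against 81–84% if 3 are. They rest on assumed adherence of 90% and 40%, daily use of Table 2, and a retained-only summary as the comparison.

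A reader might go further and say that the next phase turns on this figure. Section 1.1 says only that this is the second of three phases; no adherence target or progression criterion is given. The endpoint is descriptive, but feasibility is a stated purpose and the correction is cheap, so the change should be made.

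**What to change.** 1. Section 3.3.1: do not treat low NMES use as a reason to remove a participant from the study. Record it as the compliance outcome and keep the participant in follow-up through week 12. Leave the safety discontinuation criteria unchanged.
2. Sections 1.3 and 8.3: report compliance for every participant randomised to NMES as logged sessions divided by the sessions scheduled in Table 2 over weeks 1–6 (77 if used daily). Report physician-directed stops separately, and also show adherence up to the stop.
3. Section 3.3.2: state that data up to withdrawal will be used, and reconcile the statement on recruiting to complete data with the statement that withdrawals are not replaced.
4. Section 7.4.6.4: require device return and log download whenever NMES stops or a participant is withdrawn, not only at week 6.

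The cost is protocol wording and a few return mailers. The downside is a less favourable adherence figure.

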3.3.2 Follow-up for withdrawn subjects

Describe when and how to withdraw subjects from the study; the type and timing of the data to be collected for withdrawal of subjects; whether and how subjects are to be replaced; the follow-up for subjects withdrawn from investigational treatment.

Data collected up to the time of withdrawal may be used in the study. Subjects will be recruited until the desired number of participants with complete data points is reached. Subjects who experience AEs that are potentially related to the intervention will be followed via phone call or email to obtain information on how the AE resolves.

Participants who experience any of the above mentioned AEs will be followed up until resolved or stabilized.

Subject will be asked for consent to be contacted for possible future studies. Withdrawn subjects will be contacted if new information is available concerning the methods and techniques used in the study.

The subjects who withdraw from the study will not be replaced.

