8.0 Subject Numbers and Statistical Plan

8.1 Number of Subjects

Indicate the maximum number of subjects to be accrued/enrolled. Distinguish between the number of subjects who are expected to be enrolled and screened, and the number of subjects needed to complete the research procedures if applicable (i.e., numbers of subjects excluding screen failures.)

50 Participants will be enrolled.

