8.2 Sample size determination

If applicable, provide a justification of the sample size outlined in section 8.1 to include reflections on, or calculations of, the power of the study.

Two independent sample proportion comparison test was to compute the sample size using G* Power 3.1. A power analysis was performed based on the proportion of participants able to perform a heel rise at week 12, which is a strong predictor of long-term outcomes. With current rehabilitation strategies, 50% of participants are able to perform a single heel-rise at week 12. A clinically-significant improvement that would justify the application of the proposed treatment would be that 85% of participants would perform a heel-rise. A minimum of 22 subjects should be recruited in each group to achieve 80% power, with 5% significant level, equal allocation, to detect a significant difference between the two groups. Assuming an attrition rate similar to our previous studies of 10%, the total number of subjects in the NMES group should be 25.

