17.4 Subject Enrollment

Describe the procedures for coordination of subject enrollment and randomization for the overall project.

Clinicians collaborating in the study will identify patients at the moment of diagnosis with a complete Achilles rupture and undergoing an Achilles repair surgery at the sports medicine clinic. Clinicians will hand out the study flier and briefly mention to the patient that they may be eligible for a research study. The flier will include a QR code that will direct patients to a YouTube video where more information about the study is provided. If the participant is interested, the PI and/or a member of the team will provide an electronic copy of the informed consent for the patient to read. At the post-surgery appointment, a member of the team will discuss any details of study with the participant and will answer any questions they may have. Then the screening questions will be asked, and participants will sign the informed consent if eligible to participate.

Participants will be randomly assigned to a NMES treatment or control group in a 1:1 ratio. The Statistician will be responsible for generating a master list for each site with patient codes will be prepopulated with randomly assigned treatments (NMES vs control). As recruitment is performed, patients will be assigned a code with the corresponding intervention. The randomization will be performed at a 1:1 ratio between control and stimulation group.

Method:

1. The Statistician will generate one mutual master list (for State College and for the University of Delaware).
2. The master list will be shared with the team members in charge of recruitment through REDCap.
3. Once a subject is recruited (screened and consented), the next available code from the list will be assigned.
4. The patient will be then notified of the type of treatment they will get.

The master list will be stored and available in REDCap.

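### Section 3.3.2 gives two incompatible recruitment rules, one of which conflicts with the fixed 50; separately, no analysis set is named and removed participants have no planned week-12 heel-rise

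*Combined protocol and SAP*

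**What the plan says.** **Recruitment.** Section 3.3.2 carries two statements a few lines apart: "Subjects will be recruited until the desired number of participants with complete data points is reached" and "The subjects who withdraw from the study will not be replaced". It does not give the target number or say what makes a participant's data complete. Section 3.1 has "Subjects: 50 participants will be recruited", section 8.1 has "50 Participants will be enrolled", and section 8.3 splits this as 25 NMES and 25 control.

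**Sizing.** Section 8.2 starts from "With current rehabilitation strategies, 50% of participants are able to perform a single heel-rise at week 12", takes 85% as the improvement worth detecting, and arrives at 22 per group for 80% power at the 5% level. It then raises the NMES group to 25 for 10% attrition.

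**Who leaves, and what is collected afterwards.** Section 3.3.1 ends participation, on the physician's recommendation, for pain above 5/10 during stimulation, tendon elongation, gapping or other adverse events. It also lists departure from standard rehabilitation, non-adherence and withdrawn consent. Section 9.1 removes anyone prescribed a modified rehabilitation protocol or further surgery. For those who leave, 3.3.2 plans contact about adverse events and new information, but no heel-rise test. On their data it says only "Data collected up to the time of withdrawal may be used in the study". Section 8.3 regards losses within the 10% as negligible because the analysis tolerates unequal groups. Neither section names an analysis set or a rule for a missing heel-rise.

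**The concern.** Two things are at stake.

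The first is when enrolment ends. Under one sentence it ends at the 50th participant; under the other it ends when an unstated number have complete data, which for the primary endpoint is known only 12 weeks after surgery. Treatment is open (7.4.5), and heel-rise ability is among the data listed for review (9.2), with cumulative review every two months (9.6). In that setting the end of enrolment should not rest on a target that nobody has written down.

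The second is who is compared. Several removal reasons plausibly mark a poorer recovery, and one of them, pain during stimulation, can arise only in the NMES arm. If the odds ratio in 8.3 is computed on those who reach week 12, the randomised comparison may no longer be intact. The remark about unequal groups in 8.3 concerns how many are lost, not which participants are lost.

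**Working it through.** **1. Reproduce the plan's own number.** Inputs from 8.2: 0.50 and 0.85, 5% level, 80% power, equal allocation. Pooled-variance formula, mean proportion 0.675:

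n = [1.645 × √(2 × 0.675 × 0.325) + 0.842 × √(0.50 × 0.50 + 0.85 × 0.15)]² / 0.35²

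= [1.0895 + 0.5171]² / 0.1225 = 21.07, so 22 per arm.

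This is the one-sided version. The two-sided version gives 27, which is a separate matter from this point. Attrition: 22 / 0.9 = 24.4, so 25 per arm and 50 in total. The stated 50 is therefore a fixed-enrolment design in which losses are allowed for in advance and not replaced.

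**2. Compare the two rules.** Fixed rule: expected completers = 50 × (1 − loss). Completer rule: enrolment = target / (1 − loss), rounded up. Only the 10% loss is in the documents; the other rates are an assumed range. The target of 44 is inferred as 2 × 22. The target of 50 is an assumption.

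| Loss | Completers if 50 enrolled | Enrolment for 44 completers | Enrolment for 50 completers |
|---|---|---|---|
| 5% | 47.5 | 47 | 53 |
| 10% | 45 | 49 | 56 |
| 15% | 42.5 | 52 | 59 |
| 20% | 40 | 55 | 63 |

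On average the rules are compatible with the 50 if the target is 44 and loss stays near 10%. The documents state neither condition as the rule.

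**3. Allow for chance at the planned 10%.** Treat losses as independent, with 25 per arm. The probability of at least 44 completers out of 50 is 0.77, so in 1 − 0.77 = 0.23 of cases one rule says stop and the other says continue. The probability of at least 22 in both arms is 0.58, so if the target is read per arm the rules part in 1 − 0.58 = 0.42 of cases.

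**4. Where the fixed rule falls short of 44.** Six lost of 50 is 12% and leaves 44; seven lost leaves 43. The total drops below 44 only when loss exceeds 12%.

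**5. What a completer target would buy.** Power with 22 per arm is 0.82 one-sided or 0.71 two-sided. With 20 per arm (20% loss from 25) it is 0.78 or 0.67. The gain is about 0.04.

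**6. Selective loss within the plan's own allowance (illustration).** The allowance is 25 − 22 = 3 per arm. Suppose NMES has no effect, so 12.5 of 25 would succeed in each arm, and only the NMES arm loses three. If all three would have failed, completers show 12.5 / 22 = 56.8%. If all three would have succeeded, they show 9.5 / 22 = 43.2%. The true rate is 50% in both cases. The shift is up to 6.8 points either way, and it is the same whether or not later recruits are added under the same removal process.

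**The case against.** The best defence is that the 50 is a ceiling. The template prompt for 8.1 asks for the maximum enrolment, 3.1 and 8.3 agree on 50, and the only completer number the documents support is 22 per group. Recruiting towards 44 completers and stopping at 50 is a workable rule, and protecting the evaluable number is a legitimate aim. This is a fair reading, but it is not written anywhere. It does not remove the sentence saying withdrawals are not replaced, and it leaves the target undefined.

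A reader might also infer stronger claims that the documents do not support:

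- **The trial will exceed 50.** That needs a 50-completer target or a loss well above 10%; neither is in the documents.
- **The analysis populations contradict each other.** None is defined, so this is an omission.
- **The recruitment sentence itself enriches the completers for good recoveries.** Selection comes from the removal rules and the missing week-12 follow-up, and would be the same with exactly 50 enrolled.
- **Newcomers fail to restore the depleted arm.** Section 17.4 says "the next available code from the list will be assigned". That preserves randomisation, whereas steering newcomers to one arm would undermine it.
- **The bias favours NMES.** Nothing in the documents fixes its direction or size.

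**Conclusion.** The point holds in two parts. First, 3.3.2 contains two recruitment rules that cannot both be followed, and the completer rule is the one out of line with 3.1, 8.1, 8.2 and 8.3. At the planned 10% loss the practical gap is small if the target is 44 (49 against 50) and material if it is 50 (56 against 50). Even with a target of 44, chance alone separates the rules in about a quarter of cases, assuming independent losses.

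Second, and independently of the recruitment rule, the primary analysis set is undefined and removed participants have no planned primary outcome. A completers' comparison can therefore be selective by arm. The 6.8-point shift is an illustrative extreme for three losses in one arm, not an estimate.

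The arithmetic from 22 to 25 per arm stands. This is a correction that should be made, and most of it is cheap.

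**What to change.** 1. In 3.3.2, delete the sentence on recruiting until enough participants have complete data, and keep the one on no replacement. In 8.1 and 8.3, state that 50 means randomised participants and that enrolment ends there whatever the number of completers.
2. In 8.3, name the primary analysis set: all randomised participants, as assigned.
3. Distinguish stopping NMES from leaving the study, and reconcile 3.3.1 and 9.1 with that distinction. This concerns data collection only; it does not touch who should stop stimulation, or when.
4. Seek the week-12 heel-rise from those who stop NMES, where the physician permits the test and consent continues. The visit is already in the schedule.
5. State a rule for a missing heel-rise, for example counted as unable, with a sensitivity analysis under other assumptions.

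**Cost.** Item 1 is a one-line deletion and a clarification. Items 3 and 4 need edits to three sections, and the consent text should be checked for continued follow-up. With no replacement, fewer than 44 are evaluable if more than 6 of 50 are lost, and 22 in each arm is not assured even at 10% loss (probability 0.58). Counting missing as unable also has a price. With three random losses per arm, the planned rates become 0.85 × 22 / 25 = 74.8% and 0.50 × 22 / 25 = 44.0%, so the difference shrinks from 35 to 30.8 points. That is a reason to obtain the test wherever possible and to keep the sensitivity analysis.
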